2.8 Safety analyses

All safety analyses will be performed using the safety set. All listings will be presented by cohort, treatment group, patient and visit/time if applicable. Summary tables will be presented by cohort (including pooled cohort,) and treatment group. Additionally, if there exists a similar treatment regimen among the cohorts, safety analysis will be performed by pooling the cohorts that have used the similar treatment regimen.

2.8.1 Adverse events (AEs)

The number and percent of patients with treatment emergent adverse events will be presented. The treatment emergent adverse events (events started on or after the first dose of study medication or events present prior to the first dose of study medication but increased in severity based on preferred term on or after the first dose of study medication) will be summarized by primary System Organ Class (SOC) and Preferred Term (PT).

Adverse events will be summarized by presenting, for each treatment group, the number and percentage of patients having at least one AE, having an AE in each primary system organ class and having each individual AE (preferred term). Summaries will also be presented for AEs by severity (Toxicity grade) and for study treatment related AEs. If a patient reported more than one adverse event with the same preferred term, the adverse event with the greatest severity will be presented. If a patient reported more than one adverse event within the same primary system organ class, the patient will be counted only once with the greatest severity at the system organ class level, where applicable.

The latest MedDRA version available before the DBL will be used for reporting the adverse events and the same will be described in a footnote.

The most common adverse events reported ($\geq z$ % in any group for each preferred term in the table by SOC and PT) will be presented in the clinical study report by descending frequency according to its incidence in overall group starting from the most common event. Here threshold value z is set to 5 (%) but will be reviewed and updated as needed.

Separate summaries will be provided for study medication related adverse events, mortality, in hospital mortality, mortality related to malaria by adjudication, serious adverse events, adverse events leading to treatment discontinuation, adverse events leading to dose adjustment, and the safety stopping criteria, i.e., "All cause death or SAE possibly related to study drug". Summaries will also be provided separately for adverse events occurring during the IV study period (prior to oral standard of care, Coartem,) and for adverse events post the IV study period (after taking oral Coartem).

Serious adverse events in screening phase will be flagged in data listing due to rare frequency.

Patients who experienced a grade 3 or grade 4 AE will be summarized.

For the legal requirements of ClinicalTrials.gov and EudraCT, two required tables on treatment emergent adverse events which are not serious adverse events with an incidence greater than 5% and on treatment emergent serious adverse events and SAE suspected to be related to study treatment will be provided by system organ class and preferred term on the safety set. Five percent cut-off is to be reviewed and updated as needed prior to data base lock.

If for a same patient, several consecutive AEs (irrespective of study treatment causality, seriousness and severity) occurred with the same SOC and PT:

- a single occurrence will be counted if there is ≤ 1 day gap between the end date of the preceding AE and the start date of the consecutive AE
- more than one occurrence will be counted if there is > 1 day gap between the end date of the preceding AE and the start date of the consecutive AE
- For occurrence, the presence of at least one SAE / SAE suspected to be related to study treatment / non SAE has to be checked in a block e.g., among AE's in a ≤ 1 day gap block, if at least one SAE is occurring, then one occurrence is calculated for that SAE.

Number of deaths resulting from SAEs suspected to be related to study treatment and number of deaths resulting from SAEs irrespective of causality will be provided. Separate summaries

of deaths during initial hospitalization, post hospitalization, and post hospitalization malaria related deaths confirmed by adjudicated committee may be provided.

The adverse events and SAEs pooled from all Cohorts, if similar treatment regimen exists among the cohorts, will be summarized overall and for the subgroups defined in [Section 2.2.1](#).

Algorithms for date imputations is provided in Appendix 5.

2.8.1.1 Adverse events of special interest / grouping of AEs

The adverse events of special interest are defined in the Case retrieval Sheet (CRS) which is updated for each MEDDRA dictionary. The CRS data are stored in TMS.ECRS SAS dataset corresponding to a subset of eCRS SAS view for which the following filtering criteria are applied

- Drug code = KAE609
- the latest version of MedDRA at the time of final database lock.
- End date is null (this means this is the latest eCRS version).

Potential risks based on the current eCRS are listed in [Table 2-5](#).

The number and percent of patients with these special AEs will be summarized. In addition, listings of related adverse events will be provided.

Table 2-5 List of safety topics of interest

Risk or Adverse Reaction Name	Risk SOC	MedDRA Term	MedDRA Level	MedDRA Qualifier	MedDRA Code
Adrenal gland disorder	Endocrine disorders	Adrenal gland disorder [KAE609] (CMQ)	CMQ		90008629
Anemia	Blood and lymphatic system disorders	Haematopoietic erythropenia (SMQ)	SMQ	Broad	20000029
		Haemolytic disorders (SMQ)	SMQ	Broad	20000019
Antimalarial drug resistance	General disorders and administration site conditions	Development of clinical resistance to KAE609 in P. vivax and P. falciparum [KAE609] (CMQ)	CMQ		90008634
		Lack of efficacy (PSUR) [STANDARD] (NMQ)	NMQ		90000022
Gastrointestinal disorders	Gastrointestinal disorders	Gastrointestinal nonspecific symptoms and therapeutic procedures (SMQ)	SMQ	Narrow	20000140
Hepatotoxicity (GenMed)	Hepatobiliary disorders	Drug related hepatic disorders - comprehensive search (SMQ)	SMQ	Broad	20000006
Hypoglycemia	Metabolism and nutrition disorders	Hypoglycaemia (SMQ)	SMQ	Narrow	20000226
Inflammation	Investigations	Inflammation [KAE609] (CMQ)	CMQ		90012465
Injection site reactions	Injury, poisoning and procedural complications	ADR Injection site reaction [ADR_STD] (NMQ)	NMQ		90003467
Phototoxicity	Skin and subcutaneous tissue disorders	Photosensitivity reactions [STANDARD] (NMQ)	NMQ		90000921
QTc prolongation	Cardiac disorders	Torsade de pointes/QT prolongation (SMQ)	SMQ	Broad	20000001
Semen discoloration	Reproductive system and breast disorders	Fertility disorders-male (based on SMQ) [STANDARD] (NMQ)	NMQ	Broad	90001282

2.8.2 Laboratory data

Laboratory data for hematology and biochemistry parameters will be assessed from a point of care device. In case of non-availability of the point of care device due to any reason, local laboratory evaluation is preferred. However, statistical analysis will be based on the combined data from both types of assessments.

Descriptive statistics will be generated for all clinical laboratory tests performed (actual values and changes from baseline) for three groups of laboratory tests (hematology, clinical chemistry and urinalysis) by laboratory test and treatment group. Change from baseline will only be summarized for patients with both baseline and post baseline values and will be calculated as:

$$\text{change from baseline} = \text{post baseline value} - \text{baseline value}$$

The following laboratory parameters will be analyzed for hematology test group: hemoglobin, platelets, white blood cell count, hematocrit, red blood cell (RBC) count, lymphocytes, lymphocytes (%), monocytes, monocytes (%), eosinophils, eosinophils (%), neutrophils, neutrophils(%), basophils, and basophils (%).

The following laboratory parameters will be analyzed for Biochemistry test group: creatinine, total bilirubin (TBL), direct bilirubin, alanine aminotransferase (ALT), aspartate aminotransferase (AST), alkaline phosphatase (ALP), glucose, blood urea nitrogen (BUN), sodium, potassium, calcium, albumin, glucose, Bicarbonate, Estimated glomerular filtration rate (eGFR), lactate, LDH, and INR (in selected cases).

Box plots for selected biochemistry and hematology parameters normalized using ULN (upper limit of normal) will be provided by timepoint and treatment group.

For liver enzymes (ALT, AST, etc.), the shift table of CTCAE grades relative to baseline will be provided. For other lab parameters, the shift tables using low/normal high will be provided for each visit and a worst post-baseline value. Summary with frequency and percentage of patients with liver related events as defined in [Table 2-6](#) will be provided by treatment:

Table 2-6 Liver-related events

Parameter	Criterion
ALT	>3xULN; >5xULN; >8xULN; >10xULN; > 20XULN
AST	>3xULN; >5xULN; >8xULN; >10xULN; >20XULN
ALT or AST	>3xULN; >5xULN; >8xULN; >10xULN; >20XULN
ALT or AST and TBL	ALT or AST > 3 × ULN and TBL > 2 x ULN ALT or AST > 5 × ULN and TBL > 2 x ULN ALT or AST > 10 × ULN and TBL > 2 x ULN
TBL	>1.5xULN, >2xULN, >3XULN
ALP	>2xULN, >3xULN
ALP & TBL	ALP >3xULN & TBL >2xULN
(ALT or AST) & TBL & ALP	ALT or AST >3xULN & TBL >2xULN & ALP <2xULN

Peak ALT and AST and peak TBL will be plotted using eDISH (evaluation of Drug Induced Serious Hepatotoxicity) method and Modified eDISH (mDISH) method, see Lin, et. al. (2012).

Listing of patients with the following laboratories will be provided:

- Serum creatinine increase 25 – 49% compared to baseline
- Serum creatinine increase $\geq 50\%$ compared to baseline
- New Plasma lactate > 4 mmol/l
- New dipstick proteinuria $\geq 1+$
- New dipstick hematuria $\geq 1+$

For urinalysis, frequency tables will be presented. Number and percent of patients in each category will be presented for each visit.

Laboratory measurements, which are recorded as below the assay detection limits, will be imputed as half of the detection limit; and those above the detection limit will be imputed as within the detection limit, for the summary statistics.

Analysis of Hemolysis

Early Hemolytic anemia is defined as 10% or greater decrease in hemoglobin levels and an increase of LDH levels to >390 U/L, or an increase of $\geq 10\%$ above baseline occurring up to Day 8 of the study.

Delayed hemolytic anemia occurs > 7 days after initiation of parenteral study drug (IV artesunate or IV cipargamin) during the study period. It is defined as 10% or greater decrease in hemoglobin levels and an increase of LDH levels to >390 U/L, or an increase of $\geq 10\%$ above Day 8 value. If Day 8 value is missing, use the closest value.

The number (and proportion) of patients with early hemolysis and number (and proportion) of patients with delayed hemolysis will be summarized by phase (Early or Delayed) and visit (Early: Days 1 to 3, Days 4 to 8, Days 1 to 8; Delayed: Days 9 to 15, Days ≥ 16 , \geq Day 9), cohort, and treatment group. For delayed hemolysis, visits after Day 8 will be reported.

Besides, number and percent of patients with decrease in hemoglobin $\geq 10\%$ (from baseline for early and from Day 8 for delayed) will be summarized by phase (Early or Delayed) and visit, cohort, and treatment group.

Analysis of Lactate

A shift table presenting a shift in lactate levels from baseline to each post-baseline visit will be provided by visit, cohort, and treatment group. The following categories will be used; ≤ 2 , > 2 - <4 , ≥ 4 mmol/l.

The percentage change from baseline in lactate level will be summarized by visit, cohort, and treatment group.

Time to normalized lactate level (lactate ≤ 2 mmol/l) (in hours) in patients with baseline lactate level above normal will be summarized descriptively using the Kaplan-Meier method by cohort and treatment group. The Kaplan-Meier curve will be also presented. If for a patient the blood lactate does not normalize, the time will be censored at the last blood lactate assessment. Patients with missing baseline lactate values will be excluded.

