16.1 Appendix 1: Liver event and laboratory trigger definitions & follow-up requirements

Table 16-1 Liver event and laboratory trigger definitions

	Definition/ threshold

Liver laboratory triggers
 
If ALT, AST and total bilirubin normal at baseline:
	
 • ALT or AST > 5 × ULN • ALP > 2 × baseline (in the absence of known bone pathology) • Total bilirubin > 3 × ULN (in the absence of known Gilbert syndrome) • Potential Hy's Law cases (defined as ALT or AST ≥ 3 × ULN and Total bilirubin ≥ 2 × ULN [> 50% conjugated fraction] with no initial findings of cholestasis (i.e. ALP < 2 × ULN at baseline) and a hepatocellular pattern of injury at the time of liver injury (R ratio ≥ 5)*) • Any clinical event of jaundice (or equivalent term) • ALT or AST > 3 × ULN accompanied by (general) malaise, fatigue, abdominal pain, nausea, or vomiting, or rash with eosinophilia • Any adverse event potentially indicative of a liver toxicity
If ALT or AST abnormal at baseline:	
 • ALT or AST > 2x baseline or > 300 U/L (whichever occurs first)
*R ratio: ALT / ALP, using factor of elevation over ULN for both enzymes	

Table 16-2 Follow-up requirements for liver laboratory triggers and liver symptoms

ALT	TBL	Liver Symptoms	Action
ALT increase without bilirubin increase post dose:			
If normal at baseline: ALT > 5 x ULN If elevated at baseline: ALT > 3 x baseline	Normal TBL OR If TBL elevated at baseline : no change from baseline TBL	None	
 • No change to study treatment • Measure ALT, AST, ALP, TBIL, DBIL, INR, albumin and LDH within 48 hours and at least 1x per week thereafter until resolved • Follow-up for symptoms • Initiate close monitoring and workup for competing etiologies
ALT > 20x ULN	Normal	None	
 • Discontinue IV cipargamin and switch to IV artesunate • Continue IV artesunate based on benefit risk assessment of the investigator • Report as SAE • Measure ALT, AST, ALP, TBIL, INR, albumin and LDH in 48 hours and at least 1x per week thereafter until resolved • Follow-up for symptoms • Initiate close monitoring and workup for competing etiologies

ALT	TBL	Liver Symptoms	Action
ALT increase with bilirubin increase post dose:			

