- For **height in cm** and **SCr in mg/dL**: $\text{eGFR (ml/min/1.73 m}^2\text{)} = 0.413 \times (\text{height/SCr})$
- For **height in cm** and **SCr in $\mu\text{mol/L}$** : $\text{eGFR (ml/min/1.73 m}^2\text{)} = 36.5 \times (\text{height/SCr})$

Normal renal GFR values, as measured by inulin clearance ([Schwartz and Furth 2007](#)), are provided in [Table 16-4](#) below:

Table 16-4 **Normal GFR in children and young adults, as assessed by inulin clearance (adapted for pediatric participants included in this study)**

Age	Mean GFR \pm SD (ml/min per 1.73 m ²)
Term babies	
4-6 months	87.4 \pm 22.3
7-12 months	96.2 \pm 12.2
1-2 years	105.2 \pm 17.3
Children	
3-4 years	111.2 \pm 18.5
5-6 years	114.1 \pm 18.6
7-8 years	111.3 \pm 18.3
9-10 years	110.0 \pm 21.6
11-12 years	116.4 \pm 18.9
13-15 years	117.2 \pm 16.1
2.7-11.6 years	127.1 \pm 13.5
9-12 years	116.6 \pm 18.1
Young adults	
16.2-34 years	112 \pm 13

16.3

CCI

Table 16-5

CCI

CCI

16.4 Appendix 4: Modified version of WHO classification of signs of severe *P. falciparum* malaria

Severe malaria is defined as occurrence of one or more of the following observations, in the absence of an identified alternative cause, and in the presence of *P. falciparum* asexual parasitemia (WHO 2014)

Table 16-6 Definition of severe malaria

Signs	Definition
Impaired consciousness	A Glasgow Coma Score < 11 in adults or a Blantyre coma score < 3 in children
Prostration	Generalized weakness so that the person is unable to sit, stand or walk without assistance
Multiple convulsions	More than two episodes within 24 hours
Acidosis*	venous plasma lactate ≥ 4 mmol. Severe acidosis manifests clinically as respiratory distress – rapid, deep and laboured breathing
Hypoglycaemia	Blood or plasma glucose < 2.2 mmol (< 40 mg/dL)
Severe malarial anaemia	A haemoglobin concentration < 5 g/dl or a haematocrit of < 15% in children < 12 years of age (< 7 g/dl or < 20%, respectively, in adults) together with a parasite count > 10,000/ μ l
Renal impairment (acute kidney injury)**	Plasma or serum creatinine > 265 μ mol/L (3 mg/dL) or ≥ 3 x ULN or blood urea > 20 mmol/L
Jaundice	Plasma or serum bilirubin > 50 μ mol/L (3 mg/dL) with a parasite count > 100,000/ μ l
Pulmonary edema	Radiologically confirmed, or oxygen saturation < 92% on room air with a respiratory rate > 30/min, often with chest indrawing and crepitations on auscultation

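### SAP Table 2-6 counts liver events by fixed multiples of ULN whatever the baseline, and its Hy's-law-type row does not match the protocol's definition; a split by baseline status is a cheap improvement

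*SAP*

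**What the plan says.** SAP 2.8.2 promises a "Summary with frequency and percentage of patients with liver related events as defined in" Table 2-6. The rows are multiples of ULN for ALT, AST, total bilirubin (TBL) and ALP, alone and combined. The TBL row is ">1.5xULN, >2xULN, >3XULN"; the last row is "ALT or AST >3xULN & TBL >2xULN & ALP <2xULN". Neither table nor text asks for a new or worsened value, or says whether the baseline sample can count. SAP Table 5-10 takes the most extreme value in each post-baseline window for notable abnormalities, again with no condition on baseline.

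Protocol Table 16-1 is built differently. Its ULN-based triggers, including potential Hy's law, stand under "If ALT, AST and total bilirubin normal at baseline". The Hy's law entry requires "Total bilirubin ≥ 2 × ULN [> 50% conjugated fraction", ALP below 2xULN at baseline, "and a hepatocellular pattern of injury at the time of liver injury (R ratio ≥ 5". If ALT or AST is abnormal at baseline, the trigger is more than 2x baseline or more than 300 U/L. Table 16-2 uses ALT above 3x baseline for patients elevated at entry. Its combined rule also asks for TBL at least 2x baseline and 2xULN, with a doubling of direct bilirubin.

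Protocol 16.4, Table 16-6, lists jaundice among the signs that define severe malaria: "Plasma or serum bilirubin > 50 μ mol/L (3 mg/dL) with a parasite count > 100,000/ μ l". Section 5.2 excludes TBL above 3 mg/dL and ALT above 5xULN in Cohort 1 only.

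**The concern.** In Cohorts 2-5 raised bilirubin can be part of the disease that brings the patient into the trial, and protocol 4.5 itself notes that liver-test changes often accompany malaria. A count that ignores baseline mixes disease present at entry with change on treatment. The combined rows are read as a screen for serious drug-induced liver injury, so they suffer most.

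Elsewhere in SAP 2.8.2 baseline is respected: the listings take creatinine as an increase over baseline and restrict lactate, proteinuria and haematuria to new findings. SAP 2.8.3.2 counts only newly occurring notable vital signs.

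Liver safety is a named potential risk of cipargamin (protocol 4.5), and SAP Table 2-13 sends the categorical liver laboratories to the DMC and to the interim assessment after Cohort 2. A reader of those tables could not tell entry disease from drug effect.

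**Working it through.** The plan gives no figure to reproduce. The check is a comparison of definitions plus three short calculations.

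**1. Definitions side by side**

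| Element | SAP Table 2-6, last row | Protocol Table 16-1, potential Hy's law |
|---|---|---|
| ALT or AST | >3xULN | ≥3xULN |
| TBL | >2xULN | ≥2xULN, more than half conjugated |
| ALP | <2xULN, timing not stated | <2xULN at baseline |
| R ratio | none | ≥5 |
| Baseline ALT, AST, TBL | any | normal |

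**2. Entry bilirubin against the TBL cut-offs.** Multiple of ULN = 3 mg/dL ÷ ULN. The documents give no ULN, so a range is shown.

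| Assumed ULN (mg/dL) | 3 ÷ ULN | Cut-offs passed by a value above 3 mg/dL |
|---|---|---|
| 1.0 | 3.00 | 1.5x, 2x, 3x |
| 1.2 | 2.50 | 1.5x, 2x |
| 1.5 | 2.00 | 1.5x, 2x |
| 1.6 | 1.88 | 1.5x |
| 2.0 | 1.50 | 1.5x |

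At any ULN up to 1.5 mg/dL, persisting entry jaundice meets the >1.5x and >2xULN criteria and supplies the bilirubin half of every combined row. The first post-dose hepatic panel is at 12 h (protocol Tables 8-1 and 8-2).

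**3. R ratio admitted by the last row.** R = (ALT/ULN) ÷ (ALP/ULN). At the ALT limit of 3xULN:

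- ALP 0.5xULN: R = 6.0
- ALP 0.6xULN: R = 5.0
- ALP 1.0xULN: R = 3.0
- ALP 1.5xULN: R = 2.0
- ALP 1.99xULN: R = 1.5

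Only the first two reach 5, yet the last row accepts the whole range once ALT exceeds 3xULN. It also accepts AST alone. With ALT at 1xULN, R ≥5 would need ALP ≤ 1 ÷ 5 = 0.2xULN.

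**4. Dilution (illustration only; no test is planned).** Cohorts 2-5 have 14 + 38 + 38 + 20 = 110 patients per arm. Suppose a share b of both arms meets a given row from entry disease alone, and the drug adds the event in 5% of the others: p1 = b, p2 = b + 0.05(1 − b). Both rates are assumptions. With the usual normal approximation at two-sided 0.05,

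power = Φ{[(p2 − p1) − 1.96√(2p̄(1 − p̄)/110)] ÷ √[(p1(1 − p1) + p2(1 − p2))/110]}, p̄ = (p1 + p2)/2.

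| b | p2 | Background count per arm (110b) | Power |
|---|---|---|---|
| 0 | 0.050 | 0 | 66% |
| 0.02 | 0.069 | 2.2 | 42% |
| 0.05 | 0.0975 | 5.5 | 27% |
| 0.10 | 0.145 | 11 | 17% |

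The approximation is rough at such low rates. For a combined row b would be smaller than for a TBL row, because an enzyme elevation is needed as well.

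**The case against.** Much can be said for the plan.

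- **No protocol analysis was removed.** A reader might infer that the SAP drops conditions it was bound to apply. Protocol Tables 16-1 and 16-2 are monitoring and follow-up rules, protocol 12.5.2 promises no Hy's law tabulation, and the SAP labels no row as Hy's law. This stands: it is a mismatch of definitions.
- **The pause rule is not touched.** A reader might infer that inflated counts could halt recruitment. SAP Table 2-14 counts deaths and SAEs possibly related to cipargamin (besides rescue use), and hepatic SAEs follow the protocol tables (protocol 10.1.2). This stands.
- **Entry jaundice alone does not complete the last row.** ALT or AST must also exceed 3xULN, and bilirubin must still be raised after dosing. This stands.
- **The table is descriptive with a randomised control.** Entry jaundice is expected in both arms, so systematic bias in favour of either arm does not follow. A deliberately wide screen followed by case review is defensible. This stands, and it limits the importance of the point.
- **Other outputs use baseline.** The SAP plans change from baseline for total and direct bilirubin and the enzymes, CTCAE shifts for liver enzymes, low/normal/high shifts for other tests, a shift table for jaundice as a sign, a listing of liver abnormalities, and eDISH and modified eDISH plots. This stands in part. A high-to-high or present-to-present shift cannot show worsening, the enzyme shifts treat one analyte at a time, and the plots and listing give no counts. None counts the combined criteria by baseline status.

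**Conclusion.** The point holds as a cheap improvement. Table 2-6 does not separate liver abnormality present at entry from change on treatment, and its last row is wider than the protocol's potential Hy's law definition: it has no conjugated-fraction condition and admits R down to about 1.5 where the protocol asks for 5.

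The consequence is confined to Cohorts 2-5 as far as entry jaundice is concerned. It rests on two assumptions: a bilirubin ULN of 1.5 mg/dL or lower, and bilirubin still raised at 12 h or later. The main effect is dilution in both arms, with possible chance imbalance in arms of 14 to 38. Its size cannot be fixed, because the documents give no frequency of jaundice at entry; the power figures only show the direction and rough scale.

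**What to change.** In SAP 2.8.2:

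1. Keep the present all-patient counts of Table 2-6 and state that they use post-baseline values.
2. Show each row split by baseline status: ALT, AST and TBL all normal, against any of them abnormal. In the abnormal group, also count patients who moved to a higher Table 2-6 category than at baseline. A patient already above 3xULN for TBL at entry cannot move higher in that row, so refer the reader to the change-from-baseline summaries for such patients.
3. Add one row for potential Hy's law with the laboratory criteria of protocol Table 16-1 (direct bilirubin above 50% of total, baseline ALP below 2xULN, R ≥5). Show it by baseline status too, so that patients abnormal at entry stay in view.

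Do not import a multiple of baseline for now. Table 16-1 (more than 2x baseline or more than 300 U/L) and Table 16-2 (ALT more than 3x baseline; TBL at least 2x baseline) differ, and Table 16-1 gives no multiple for abnormal baseline bilirubin. The sponsor should reconcile the two tables.

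ALT, AST, ALP, total and direct bilirubin are already collected (protocol Table 8-5), so the cost is SAP wording, some programming and a larger table. No present count is lost.

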10.2.2 Renal safety monitoring

Once a participant is exposed to study treatment, renal laboratory alerts or renal safety events should be monitored and followed up by the investigator or designated trial staff as summarized in [Table 16-3](#) and [Table 16-4](#).

Abnormal renal findings must be confirmed within 24-48 hours after the first assessment.

Renal events in the pediatric population should be defined as 25% decrease in eGFR using age-specific normal values for eGFR and serum/urinary normal values. The Schwartz age-specific eGFR formula ([Schwartz and Furth 2007](#)) is commonly used to estimate eGFR in the pediatric population. Refer to [Section 16.3](#) for Schwartz formula calculation guidance, and normal age-related pediatric eGFR values. Due to the low values of serum creatinine, small changes can be interpreted as substantial changes in eGFR which can be ignored if eGFR is $> 90 \text{ ml/min/1.73 m}^2$.

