16.2 Appendix 2: Specific Renal Alert Criteria and Actions and Event Follow-up

Table 16-3 Specific Renal Alert Criteria and Actions

Renal event	Actions
Confirmed serum creatinine increase 25 – 49%	
 Consider causes and possible interventions Follow-up within 24-48 h
Serum creatinine increase $\geq 50\%$ *OR if <18 years old , $\text{eGFR} \leq 35 \text{ ml/min/1.73 m}^2$	
 Consider causes and possible interventions Repeat assessment within 24-48h Consider drug discontinuation unless other causes are diagnosed and corrected Consider patient hospitalization and specialized treatment
New onset dipstick proteinuria $\geq 3+$	
 Consider causes and possible interventions Assess serum albumin & serum total protein Repeat assessment to confirm within 24-48h Consider drug discontinuation unless other causes are diagnosed and corrected
New onset hematuria $\geq 3+$ on urine dipstick	
 Repeat assessment to confirm within 24-48h Distinguish hemoglobinuria from hematuria Urine sediment microscopy Assess sCr Exclude infection, trauma, bleeding from the distal urinary tract/bladder, menstruation Consider bleeding disorder
+ Corresponds to KDIGO criteria for Acute Kidney Injury	

Follow-up of renal events:

Assess, document and record in CRF:

- Urine dipstick and sediment microscopy: crystals, red blood cells (dysmorphic/glomerular vs. non-dysmorphic/non-glomerular), white blood cells, tubular epithelial cells
- Blood pressure and body weight
- Serum creatinine, BUN, electrolytes (sodium, potassium, calcium) and bicarbonate
- Urine output

Whenever a renal event is identified, a detailed participant history and examination are indicated to identify and potentially eliminate risk factors that may have initiated or contributed to the event:

- Blood pressure assessment (after 5-minute rest)
- Signs and symptoms like fever, headache, shortness of breath, back or abdominal pain, dysuria or hematuria, dependent or periorbital edema
- Changes in blood pressure, body weight, fluid intake, voiding pattern, or urine output

- Concomitant events or procedures such as trauma, surgical procedures, cardiac or hepatic failure, contrast media or other known nephrotoxin administration, or other diseases or causes, e.g., dehydration due to delirium

Pediatric participants: special considerations

Schwartz formula:

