Key signs of Severe Malaria are Altered consciousness, Renal impairment, Acidosis, and Respiratory distress.

Signs of severe malaria

The following signs of severe malaria will be monitored at every visit during the entire study duration.

- **Altered consciousness** – Prostration (inability to sit or drink or breast feed) or GCS < 11 for patients > 5 years / BCS < 3 for patients ≤ 5 years of age
- **Renal Impairment** - Serum creatinine > 3xULN or > 3 mg/dL or need for renal replacement therapy (RRT)
- **Acidosis** - Plasma lactate > 4 mmol/L or Respiratory distress.
Respiratory distress is defined as rapid, deep and labored breathing (costal indrawing, use of accessory muscles and nasal flaring)- present or absent.
In database, Plasma lactate is captured under lactic acid.
- **Severe anemia** - Hb < 5 g/dl or Hb < 7g/dl in pediatric and adults respectively or need of blood transfusion
- **Jaundice** - Serum bilirubin > 3 mg/dl
- **Hypoglycemia**- plasma glucose < 40 mg/dL
- **Blantyre coma scale (BCS)** is a number from 0 to 5 based on [Appendix 5, Table 5-1](#) for patients ≤ 5 years. The score is determined by adding the results from three categories: Motor response, verbal response, and eye movement. The minimum score is 0 which indicates poor results while the maximum is 5 indicating good results.

- **Glasgow Coma Scale (GCS)** is a clinical scale used to reliably measure a person's level of consciousness for age > 5 years. The score is determined by adding the results from three categories: Motor response, verbal response, and eye movement. A person's GCS score can range from 3 (completely unresponsive) to 15 (responsive) based on [Appendix 5, Table 5-2](#).

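### The renal laboratory listing in SAP 2.8.2 omits the protocol's eGFR ≤35 alert for participants under 18, so some paediatric alerts are not picked out or show only in the lower creatinine band

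*SAP*

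**What the plan says.** Protocol 16.2 (Table 16-3) sets four rows of renal alerts. The first is a confirmed creatinine rise of 25–49%. The second is a rise of 50% or more, with an alternative that begins "OR if <18 years old" and sets eGFR at 35 ml/min/1.73 m² or less. This row asks the investigator to repeat the test within 24–48 hours and to consider stopping the drug and hospitalising the patient. The third row is "New onset dipstick proteinuria" at 3+ or more, and the fourth is new haematuria at 3+ or more. Protocol 10.2.2 directs sites to follow renal alerts by this table.

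SAP 2.8.2 specifies a listing of patients who meet any of these: "Serum creatinine increase 25 – 49% compared to baseline", a creatinine rise of 50% or more, new plasma lactate above 4 mmol/l, "New dipstick proteinuria" at 1+ or more, and "New dipstick hematuria" at 1+ or more. None of the lines uses eGFR or age.

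Elsewhere in SAP 2.8.2, eGFR is among the biochemistry parameters to be analysed ("Estimated glomerular filtration rate (eGFR), lactate, LDH, and INR (in selected cases"). It therefore gets descriptive statistics and the generic low/normal/high shift table, with no cut at 35. SAP Section 4 records no change from the protocol-specified analyses.

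**The concern.** The listing carries both creatinine bands of Table 16-3, and carries the dipstick findings at a wider threshold. The one Table 16-3 criterion with no counterpart is the one written for minors. An absolute eGFR limit matters most when kidney function is already reduced at entry, because a modest percentage rise in creatinine can then take a child below it.

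Low baseline eGFR is plausible in this trial. Renal impairment is a qualifying sign of severe malaria for Cohorts 2–5 (Protocol Table 16-6), and the renal-disease exclusion in Protocol 5.2 covers only illness unrelated to the malaria episode. At least 192 of the 252 planned participants are under 12, and any aged 12–17 in Cohorts 1–2 add to that.

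At stake is whether the safety output identifies every paediatric renal alert that the protocol itself defines. An analyst who follows SAP 2.8.2 as written would not produce that identification.

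**Working it through.** **Inputs.** Schwartz formula from Protocol 16.2: eGFR = 0.413 × height (cm) / creatinine (mg/dL). Alert limit of 35 and bands of 25–49% and ≥50% from Table 16-3 and SAP 2.8.2. Median heights from SAP Tables 5-13 and 5-14. The plan states no figure for this point, so there is none to reproduce.

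**Step 1: baseline ranges affected.** With height constant over the four-week study, eGFR after dosing = baseline eGFR / (1 + fractional creatinine rise). The baseline that lands exactly on 35 is 35 × (1 + rise):

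- rise of 25%: 35 × 1.25 = 43.75
- rise of 50%: 35 × 1.50 = 52.5

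This gives three cases for a minor who starts above 35:

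| Baseline eGFR | Can reach ≤35 on | Where the SAP listing shows it |
|---|---|---|
| below 43.75 | a rise under 25% | not picked out |
| below 52.5 | a rise of 25–49% | lower band only |
| 52.5 or more | only a rise of ≥50% | ≥50% line, as in the protocol |

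**Step 2: examples.**

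- Boy of 6 years, 115.66 cm, creatinine 1.2 to 1.4 mg/dL: 0.413 × 115.66 / 1.2 = 39.8, then / 1.4 = 34.1. The rise is 16.7%: a protocol alert, not picked out.
- Same boy, 1.0 to 1.4 mg/dL: eGFR 47.8 to 34.1. The rise is 40%: second row in the protocol, lower band in the listing.
- Boy of 2 years, 86.45 cm, 0.9 to 1.1 mg/dL: eGFR 39.7 to 32.5. The rise is 22.2%: not picked out.

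**Step 3: does the renal-impairment sign fill the gap?** SAP 2.1.1 defines it as "Serum creatinine > 3xULN or > 3 mg/dL or need for renal replacement therapy (RRT"). Creatinine at eGFR 35 is 0.413 × height / 35, and eGFR at 3 mg/dL is 0.413 × height / 3:

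| Child | Height (cm) | Creatinine at eGFR 35 (mg/dL) | eGFR at 3 mg/dL |
|---|---|---|---|
| Girl, 6 months | 65.73 | 0.78 | 9.1 |
| Boy, 6 years | 115.66 | 1.36 | 15.9 |
| Boy, 11 years | 143.73 | 1.70 | 19.8 |

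The absolute limit is far beyond the alert. The 3×ULN limit would cover it only if the ULN in use were below one third of the third column, about 0.26, 0.45 and 0.57 mg/dL. The documents give no ULN.

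**Step 4: how many.** No frequency is given. As an assumption only, if 1%, 5% or 10% of the 192 children under 12 enter with eGFR between 35 and 52.5, the pool at risk is 1.9, 9.6 or 19.2, so about 2, 10 or 19. Each must also worsen to 35 or below, on a rise under 50%, to be affected. These are pool sizes, not expected counts.

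**The case against.** The strongest reply is that nothing is lost from the data. SAP 5.2.4 says that the listings show all collected data, SAP Table 2-12 provides a listing for biochemistry, and Protocol 12.5.2 flags and lists abnormal laboratory values where normal ranges exist. A child's eGFR of 34 will therefore be in the listings. SAP 2.8.2 also never claims to reproduce Table 16-3: it adds lactate, widens the dipstick cuts and drops the confirmation requirement. A child with a 40% rise is correctly placed in a band defined by creatinine alone. All of this stands. What is missing is the identification of such a value as a protocol alert, not the value.

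Three stronger readings are tempting, and the documents do not support them.

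- A reader might infer an effect on efficacy, because safety concerns under Protocol 16.2 can lead to IV artesunate rescue, rescue before 48 hours counts as non-success, and rescue use feeds the pause criterion. Those decisions follow Table 16-3 at the site, where the eGFR limit is intact. A listing line cannot change them.
- A reader might infer that alerts go unnoticed during the trial. The site-level alert still operates, and the pause rule counts deaths, possibly related serious events and rescue use, not eGFR.
- A reader might infer that the paediatric definition in Protocol 10.2.2 ("Renal events in the pediatric population should be defined as 25% decrease in eGFR using age-specific normal values") is missed too. Measured from the child's own baseline, a 25% fall is a creatinine rise of 1/0.75 − 1 = 33.3%, which the 25–49% line already catches.

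**Conclusion.** The point holds as a narrow gap in safety reporting. The SAP 2.8.2 listing takes the creatinine bands of Table 16-3 and leaves out the alternative for minors in the ≥50% row. Participants under 18 with baseline eGFR above 35 and below 52.5 can meet the protocol alert and either not be picked out (possible below 43.75) or appear only in the lower band. Inference, rescue, 48-hour clinical success and the pause rules are untouched.

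The baseline limits rest on the protocol's Schwartz formula and constant height. How often this will happen is unknown. The case for acting is that the criterion is the protocol's own, most of the trial is paediatric, and the change costs almost nothing.

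**What to change.** In SAP 2.8.2, add one line to the listing, by arm, for participants under 18: post-baseline eGFR ≤35 ml/min/1.73 m², new since baseline, grouped with the ≥50% creatinine line. Mark separately those already at or below 35 at baseline.

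State one eGFR source for this flag: 0.413 × screening height (cm) / creatinine (mg/dL), as in Protocol 16.2. Protocol Table 8-5 also takes eGFR from the point-of-care device, so note any difference between the two values.

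The cost is one derived flag in an existing listing. Creatinine and eGFR are already analysed, height is measured at screening, and the SAP text already reflects an update after Cohorts 1 and 2. No protocol amendment is needed. The reference in Protocol 10.2.2 to Section 16.3 for the Schwartz formula, which is in 16.2, is clerical and can be corrected whenever the protocol is next amended.
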